### 8.2 Secondary Analysis

Secondary analyses will include non-parametric paired comparisons between low sodium and high sodium diets of continuous outcome measures (outlined in section 7.3). Secondary comparisons might also assess differences in the dietary sodium induced changes between POTS patients and control subjects.

### 8.3 Sample Size Calculation

As this is a pilot study, there are no preliminary data available on the RH-PAT index in different sodium diets. Published data indicate that the RH-PAT index in 39 healthy subjects without endothelial function is  $1.78 \pm 0.08$  (mean  $\pm$  SEM). In the same study, RH-PAT  $< 1.35$  was found to be the best discriminator of coronary endothelial function. We will designate a more conservative  $\Delta$ RH-PAT = 0.25 as a clinically significant difference between high sodium diet vs. low sodium diet for the entire group. We expect the standard deviation around the difference will be 0.5 (based on the above data), for an effect size of 0.5. With the aforementioned assumptions for a paired test of continuous data, and a 0.05 two-sided significance level, a sample size of 44 (combined POTS patients and control subjects) would give 90% power to detect this difference. To account for drop-outs, we propose to enroll up to 50 subjects in total from the parent study. Using the same assumptions, 33 subjects would give 80% power to detect the same difference (in case of enrollment difficulties for this sub-study).

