## 5.0 INCLUSION/EXCLUSION CRITERIA

### 5.1 Inclusion Criteria

- Subjects will be enrolled in the parent study “Dietary Salt in Postural Tachycardia Syndrome” funded by R01 HL102387
- Postural Tachycardia Syndrome
  - Diagnosed with postural tachycardia syndrome by the Vanderbilt Autonomic Dysfunction Center
    - Increase in heart rate  $\geq 30$  beats/min with position change from supine to standing (10 minutes)
    - Chronic symptoms consistent with POTS that are worse when upright and get better with recumbence
- Control Subjects
  - Healthy, non-obese, non-smokers without orthostatic tachycardia
  - Selected to match profiles of POTS patients (gender, age)
  - Not using vasoactive medication
- Age between 18-60 years
- Male and female subjects are eligible.
- Able and willing to provide informed consent

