## 8.0 STATISTICAL CONSIDERATIONS

### 8.1 Primary Analysis

The primary outcome measure will be the RH-PAT index. The primary analysis will involve a non-parametric, paired, Signed Rank test of RH-PAT between all subjects (POTS patients and control subjects) on the high sodium diet vs. the low sodium diet.

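### Section 8.3 credits the SD of the paired diet difference (0.5) to data that give only a between-subject SD, and states power for a paired t-test rather than the planned signed-rank test

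*Combined protocol and SAP*

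**What the plan says.** Section 8.3 (Sample Size Calculation) first concedes that "there are no preliminary data available on the RH-PAT index in different sodium diets". It then turns to one published group: "Published data indicate that the RH-PAT index in 39 healthy subjects without endothelial function is" 1.78 with an SEM of 0.08. From this it moves to the input that drives the calculation: "We expect the standard deviation around the difference will be 0.5 (based on the above data), for an effect size of 0.5". The target difference is 0.25 and the test is two-sided at 0.05.

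Three sample-size statements follow:

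- Main target: "a sample size of 44 (combined POTS patients and control subjects) would give 90% power to detect this difference".
- Enrolment: "To account for drop-outs, we propose to enroll up to 50 subjects in total from the parent study".
- Fallback if recruitment is difficult: "Using the same assumptions, 33 subjects would give 80% power to detect the same difference".

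Section 8.1 (Primary Analysis) names the test: "The primary analysis will involve a non-parametric, paired, Signed Rank test of RH-PAT between all subjects (POTS patients and control subjects"), high against low sodium. Section 5.1 (Inclusion Criteria) admits both healthy controls and patients "Diagnosed with postural tachycardia syndrome by the Vanderbilt Autonomic Dysfunction Center".

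**The concern.** A paired comparison depends on the SD of the within-person difference. A mean and SEM from one group, each person contributing one value, describe how people differ from one another. They cannot show how far the same person's value moves between two diets. Section 8.3 nevertheless presents the 0.5 as drawn from those data, so a planning assumption reads as an empirical estimate. The source group is also healthy, while the analysed sample pools POTS patients and controls.

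Every power figure for the primary outcome rests on this number. The fallback of 33 is the most exposed, because it is the figure that would be relied on if recruitment fell short and it has no margin.

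A smaller issue is that Section 8.3 refers only to a generic paired test of continuous data, while the primary analysis is a signed-rank test. If the power figures belong to another test, they do not describe the planned analysis exactly.

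**Working it through.** **Inputs.** From Section 8.3: SEM 0.08, n = 39, difference 0.25, SD of the difference 0.5, two-sided alpha 0.05, sample sizes 33, 44 and 50. From Section 8.1: signed-rank test, all subjects pooled. The documents give no within-subject correlation, no test-retest SD and no distribution for the differences. Values used for those below are assumptions.

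**Step 1. Reproduce the plan's power.** Paired t-test, noncentral t with n − 1 degrees of freedom and noncentrality (0.25/0.5) × √n:

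- n = 44: 90.0% (stated 90%)
- n = 33: 79.5% (stated 80%)
- n = 50: 93.4% (no power stated)

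The normal approximation gives 91.3% at 44 and 81.9% at 33, a poorer match. The stated figures are paired-t figures and reproduce correctly.

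**Step 2. Trace the 0.5.** SD = SEM × √n = 0.08 × √39 = 0.4996. This is the between-subject SD of the index and coincides with the value used for the difference. The other figure cited from the same study, the 1.35 cut-off, carries no information on spread.

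**Step 3. What the substitution implies.** With equal variances on both diets, SD_diff² = 2 × SD² × (1 − ρ), so ρ = 1 − SD_diff²/(2 × SD²).

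- SEM 0.080: SD 0.4996, ρ = 1 − 0.25/(2 × 0.2496) = 0.50
- SEM 0.075 (lower rounding limit): SD 0.468, ρ = 0.43
- SEM 0.085 (upper rounding limit): SD 0.531, ρ = 0.56

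Setting the SD of the difference to 0.5 is thus the same as assuming a correlation of about 0.5 between diets.

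**Step 4. Power of the planned test on the plan's own SD.** Signed-rank test with exact two-sided critical values, simulated with at least 400,000 normal samples per cell, mean difference 0.25, SD 0.5:

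| n | Paired t | Signed-rank |
|---|---|---|
| 33 | 79.5% | 77–78% |
| 44 | 90.0% | 89% |
| 50 | 93.4% | 92% |

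The test itself costs about 2 points at 33 and about 1 point at 44 and 50. A further half point of the gap to 80% at 33 is the rounding of 79.5%. Signed-rank power reaches 80% at 35 subjects and 90% at 46, both within the planned enrolment of up to 50.

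**Step 5. Dependence on the shape of the differences.** Signed-rank power at n = 33, SD still 0.5: uniform 72%, normal 77–78%, t with 10 df about 80.5%, logistic 82%, t with 5 df 86%, Laplace 88%.

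**Step 6. Dependence on the SD of the difference.** Signed-rank, normal differences:

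| SD_diff | n = 33 | n = 44 | n = 50 |
|---|---|---|---|
| 0.45 | 85% | 94% | 96% |
| 0.50 (plan) | 77–78% | 89% | 92% |
| 0.55 | 69% | 82% | 87% |
| 0.60 | 62% | 75% | 80% |

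In terms of an assumed correlation, with SD 0.50 on each diet: ρ = 0.25 (SD_diff 0.612) gives 60%, 74% and 79%; ρ = 0.7 (SD_diff 0.387) gives 94%, 98% and 99%.

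**The case against.** The best defence is that the plan is open about its position. It calls the study a pilot, says no diet data exist, and introduces the SD as an expectation. Its arithmetic reproduces. A correlation of 0.5 is not shown to be unreasonable, and paired-t power is a common approximation for a signed-rank test. Much of this stands. The value 0.5 is not shown to be wrong, there is no calculation error, and the test-choice effect is small. What does not stand is the attribution: lacking paired data explains an assumption, but not crediting it to data that cannot supply it.

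A reader might go further and infer that the fallback of 33 necessarily misses 80% for the planned test. The documents do not support that. They state no distribution for the differences, and at SD 0.5 mildly heavy tails (t with 10 df, logistic) bring signed-rank power to 80% or slightly above. The shortfall belongs to the normal case, which the paired-t figures implicitly assume; a flatter distribution such as the uniform would make it larger.

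**Conclusion.** Wrong as written, of minor severity. The stated source of the SD of the difference cannot provide it. The 0.5 is an assumption equivalent, under equal variances, to a within-subject correlation of about 0.5 (0.43 to 0.56 allowing for rounding of the SEM), which the plan neither states nor supports.

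It may be tempting to conclude that the trial is underpowered or needs more subjects. Neither follows: with no paired information in the documents, the true SD of the difference could lie on either side of 0.5, and power could be higher or lower than claimed.

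The mismatch between tests is real but secondary, and its size is conditional on normal differences with SD 0.5. Uncertainty in the SD matters far more than the choice of test: over an illustrative SD range of 0.45 to 0.60, signed-rank power at 33 runs from about 85% to 62%.

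**What to change.** Reword the one paragraph in Section 8.3:

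1. Identify 0.50 as the between-subject SD of the RH-PAT index in the cited healthy group, and remove the statement that those data are the source of the SD of the difference.
2. Label the SD of the difference of 0.5 as an assumption, give the correlation it implies (about 0.5 with equal variances), and note that the cited group is healthy while the sample mixes POTS patients and controls.
3. Restate power for the signed-rank test, naming the conditions (normal differences, SD 0.5): about 77–78% at 33, 89% at 44 and 92% at 50. Add a short sensitivity range, for example SD 0.45 to 0.60, which gives about 85% to 62% at 33.
4. Present 33 subjects as a fallback with roughly 77–80% power, conditional on the assumed SD and distribution, rather than as an assured 80%.

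Sample size, test and procedures do not change. The only cost is a power statement that is slightly less favourable and openly conditional.

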## 9.0 RISKS & INCONVENIENCES

1. Having blood drawn may hurt, may cause bruising and may cause lightheadedness or rarely fainting.
2. The finger probes may be tight and uncomfortable.
3. The blood pressure cuffs may be uncomfortable.

## **10.0 DATA & SAFETY PLAN**

### **10.1 Adverse Event (or Unanticipated Problem) Reporting**

Any adverse events of a serious nature will be reviewed immediately with the principal investigator. Serious adverse events will be reported in writing to the Vanderbilt IRB per IRB regulations. All non-serious adverse events will be summarized once a year, during the annual review to the IRB. [name] MB ChB will be responsible for tracking adverse events in this study.

The adverse event will be described with the following information: description of the event, outcome of the event, how long it lasted, relationship to study medications, whether the event required treatment or intervention, and the outcome.

The definition of events is as follows:

Mild – transient and mild in nature, with no treatment necessary.

Moderate – some intervention and treatment necessary, but subject completely recovers.

Severe – an event that results in hospitalization, disability, death or is life threatening.

The investigator will state his opinion as to whether there is a reasonable possibility that the event or experience is related to the drug.

### **10.2 Data and Safety Monitoring**

There will be no external Data and Safety monitoring committee for this study.

## **11.0 STUDY WITHDRAWAL or DISCONTINUATION**

### **11.1 Principal Investigator Initiated Withdrawal**

The principal investigator reserves the right to withdraw the subject from the study after they have provided informed consent, but before study completion. This could occur for one of many reasons, which include, but are not limited to: non-compliance with the protocol, a concern for subject safety, the availability of new knowledge that might affect continued participation in the study, or study termination.

### **11.2. Study Subject-Initiated Withdrawal**

Subjects are free to withdraw from this study at any time. Withdrawal of consent or refusal to participate will not prejudice their health care.

## **12.0 COMPENSATION**

Subjects will be compensated \$25 for their time and inconvenience.

## **13.0 PRIVACY & CONFIDENTIALITY ISSUES**

Protected Health Information will be used in this study. The investigators will comply with the patient privacy guidelines of Vanderbilt University Medical Center and the rules outlined by the Health Insurance Portability and Accountability Act (HIPAA).

The research team is comprised of experienced research nurses and research assistants who are aware of the importance of confidentiality of health information. Research records will be stored in a locked office. Digital records will be stored on password-protected computers/servers. Digital data files will be coded so that the subject name is not in the filename or other such identifiers.

Every effort will be made to publish and present the data from this study. At no time will any subject be identified in any such publication.

## **14.0 FOLLOW-UP AND RECORD RETENTION**

### **14.1 Follow-Up**

There will be no further study follow-up after the physiological breathing study is completed.

### **14.2 Record Retention**

Study records will be kept for at least 7 years following the publication or presentation of the data collected as part of this study.

## **15.0 Study Support**

Study costs will be funded from R01 HL102387.

